- Idarubicin 12 mg/m²/day by slow (10 to 30 minutes) IV injection/infusion daily on Days 1 and 2
- Cytarabine 100 mg/m²/day by continuous 24-hour IV infusion on Days 1-5.

Group 2: Idarubicin + Cytarabine + plus lower dose CX-01

- CX-01 given as a 4 mg/kg initial bolus on Day 1, 30 minutes after completion of administration of the first dose of idarubicin followed by CX-01 0.125 mg/kg/hour as a continuous 24-hour IV infusion on Days 1-5
- Idarubicin 12 mg/m²/day by slow (10 to 30 minutes) IV injection/infusion daily on Days 1 and 2
- Cytarabine 100 mg/m²/day by continuous 24-hour IV infusion on Days 1-5.

Group 3: Idarubicin + Cytarabine + plus higher dose CX-01

- CX-01 given as a 4 mg/kg initial bolus on Day 1, 30 minutes after completion of administration of the first dose of idarubicin followed by CX-01 0.25 mg/kg/hour as a continuous 24-hour IV infusion on Days 1-5
- Idarubicin 12 mg/m²/day by slow (10 to 30 minutes) IV injection/infusion daily on Days 1 and 2
- Cytarabine 100 mg/m²/day by continuous 24-hour IV infusion on Days 1-5.

Consolidation Therapy

Evaluation for remission will take place at the time of count recovery, or, if no count recovery is achieved, at approximately Day 35 if the patient received one induction course or approximately Day 49 if the patient received re-induction course. Count recovery is defined as ANC >1,000/μL and platelet count of >100,000/μL. Remission will be defined according to IWG criteria (Appendix A). For patients with documented CR, confirmatory bone marrow aspirate slides will be submitted to the Sponsor or designee.

Patients in remission at the end of induction may proceed to consolidation therapy on study, depending upon factors including, but not limited to, European Leukemia Net (ELN) (70) genetic risk and co-existing conditions.

Patients who are not in CR at the end of re-induction will be taken off study and will complete Early Termination Visit as per Table 6—1.

Patients who could benefit from and are eligible to undergo stem cell transplantation will go off the study at any time when transplant is feasible.

Patients will receive up to two cycles of consolidation therapy on study, per NCCN guidelines, depending upon factors including, but not limited to, ELN genetic risk and co-existing conditions. A cycle of consolidation therapy is defined as the time from initiation of chemotherapy on Day 1 until count recovery.

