6.6.3 Safety Assessments

Key safety endpoints will be assessed by review of summaries of AEs which will include only treatment-emergent AEs (TEAEs), unless otherwise stated. Adverse events will be categorized by System Organ Class (SOC) and preferred term using the Medical Dictionary for Regulatory Activities (MedDRA) dictionary (version 14.1), and will be graded according to NCI-CTCAE version 4.03.

6.6.3.1 *Adverse Events*

Adverse events will be monitored throughout the study. Adverse events will be collected from the time of informed consent and continue until 30 days after the last study treatment is administered. Longer follow-up and collection of AEs may be required for patients who do not have an ANC recovery by Day 42 (i.e., until the recovery or until a reason for no recovery is diagnosed) after the last induction or consolidation cycle.

For the purpose of this study, the terms toxicity and AE are used interchangeably.

6.6.3.2 *Definitions*

6.6.3.2.1 *Definition of an Adverse Event*

In a clinical study, an AE is any untoward medical occurrence (i.e., any unfavorable and unintended sign [including abnormal laboratory findings], symptom, or disease) in a patient or clinical investigation subject after providing written informed consent for participation in the study. Therefore, an AE may or may not be temporally or casually associated with the use of a medicinal (investigational) product.

A surgical procedure that was planned prior to the start of the study by any physician treating the subject should not be recorded as an AE (however, the condition for which the surgery is required may be an AE).

In the following differentiation between medical history and AEs the term “condition” may include abnormal symptoms, diseases, laboratory, or vital sign findings.

- Conditions that started before signing of ICF and for which no symptoms or treatment are present until signing of ICF are recorded as medical history (e.g.,

seasonal allergy without acute complaints)

- Conditions that started before signing of ICF and for which symptoms or treatment are present after signing of ICF, at unchanged frequency and/or intensity, are recorded as medical history (e.g., allergic pollinosis)
- Conditions that started or deteriorated after signing of informed consent will be documented as AEs.

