6.8.2 Patient Populations Analyzed

The analysis sets that will be used for statistical analyses are as follows:

Intent-To-Treat (ITT): All randomized patients. Patients will be analyzed according to the treatment to which they are randomized. The ITT Population will be the primary analysis set for the efficacy variables.

Per Protocol (PP): Supporting analyses will be conducted on the PP Population, comprising all patients randomized and treated without major protocol violations during the trial. This population will be documented before final database lock.

Safety: All patients who received at least one dose of study treatment. Patients will be included in the analyses according to the treatment they received. The Safety Population will be used in the analyses of all safety endpoints.

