6.8.10 Safety Analysis

Safety analysis will be descriptive based on the Safety Population and will involve examination of descriptive statistics and individual patient listings for effects of study treatment on clinical safety and tolerability. The safety assessment period is from the first dose of study treatment until 30 days following the last dose of study treatment.

6.8.10.1 *Adverse Events*

All AEs will be categorized by SOC and Preferred Term using the MedDRA dictionary

and graded according to NCI-CTCAE v4.03. Treatment-emergent AE summaries will include NCI-CTCAE Grade 3 or higher AEs, and AEs resulting in discontinuation of study treatment, AEs resulting in death, deaths during the treatment period within 30 days of the last study treatment, deaths reported beyond 30 days that are considered study drug-related, and the incidence of laboratory values with NCI-CTCAE Grades 3 or 4. Particular attention will be upon coagulation parameters and bleeding-related events.

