7.4.2 Prior, Post treatment (anti AML) and Concomitant Medications

Medications received prior to or concomitantly with treatment will be coded using the WHO Drug Dictionary [March 2016 132 version] Anatomical Therapeutic Chemical (ATC) Classification codes.

Prior, post treatment medications and concomitant medications are defined as follows:

- Concomitant medications are those with a start date on or after the first dose date of study treatment, or those with a start date before the first dose date of study treatment and a stop date on or after the first dose date of study treatment.
- Prior medications will be defined as non-study medication with a stop date prior to the first dose of study treatment.
- Post treatment medications are those with start date after the last dose of study drug.

Concomitant medications will be further divided according to whether they were started before (both prior and concomitant) or after (concomitant-only) the first dose of treatment.

If a medication cannot be classified as "prior" or "concomitant" after applying imputation rules for missing/incomplete dates, it will be classified as concomitant.

Prior anti-AML treatment medications and concomitant medications will be listed and summarized separately for ITT analysis population. Post treatment medications will be listed only.

The number and percentage of subjects using each medication will be displayed together with the number and percentage of subjects using at least one medication within each therapeutic class (ATC-Level 2), chemical subgroup (ATC-Level 4), and generic term.

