7.7 Safety

7.7.1 Adverse Events

All adverse events (AEs) recorded on the eCRF will be coded using the MedDRA dictionary [Version 14.1] and classified as either pre-treatment AEs or treatment-emergent AEs (TEAEs) as follows:

- Pre-treatment AEs are events that start prior to the date of first dose of study treatment.
- Treatment-emergent AEs (TEAEs) are events with start date and time on or after the date and time of first dose of study treatment (and up to 30 days after date of last dose of treatment) with

Statistical Analysis Plan

Version: Final

Date of Issue: 20 March 2018

Cantex Pharmaceuticals, Inc. Protocol No. CNTX-CX-01 2015 AML I Covance Study ID: 00000014620 I

start date prior to the date of first dose of study treatment whose severity worsens on or after the date and time of first dose of study treatment.

Assessment of AE severity will be based on the National Cancer Institute-Common Terminology Criteria for Adverse Events (NCI-CTCAE, version 4.0.3).

All AE data will be listed by treatment group including Pre-treatment AEs and TEAEs. The number and percentage of subjects reporting each treatment AE and TEAEs will be summarized for each treatment group and overall, by System Organ Class (SOC) (sorted alphabetically) and Preferred Term (**PT**) (sorted by descending overall total) for Safety populations.

In addition, corresponding listings of serious AEs (SAEs), AEs leading to discontinuation of treatment, AEs causing interruptions from study treatment, AEs causing dose reduction from study treatment and study treatment-related AEs causing dose reductions are provided.

An overview table will summarize the number and percentage of subjects with at least one of the following AEs/TEAEs, where subjects with more than one AEs/TEAE in a particular category are counted only once in that category:

- any AE;
- any TEAEs;
- treatment-related TEAE;
- any AE by maximum NCI-CTCAE grade; treatment-related TEAE by maximum NCI-CTCAE grade;
- AE leading to treatment interruption;
- treatment-emergent AEs leading to treatment interruption;
- AE leading to treatment reduction;
- treatment-emergent AEs leading to treatment reduction;
- AE leading to treatment discontinuation; treatment-emergent AEs leading to discontinuation from the study;
- SAE;
- treatment-emergent SAE;
- SAE leading to death;
- treatment-emergent SAE leading to death;
- SAE leading to treatment discontinuation;

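### The treatment-emergent window has no split at the start of non-protocol anti-AML therapy, so toxicity of later treatment can enter the by-arm safety tables

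*Protocol*

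**What the plan says.** Three rules set the same limit.

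- Analysis period, protocol 6.8.10: "The safety assessment period is from the first dose of study treatment until 30 days following the last dose of study treatment".
- AE collection, protocol 6.6.3: "Adverse events will be collected from the time of informed consent and continue until 30 days after the last study treatment is administered". One extension is allowed: "Longer follow-up and collection of AEs may be required for patients who do not have an ANC recovery by Day 42".
- TEAE definition, SAP 7.7.1: onset from the first dose "and up to 30 days after date of last dose of treatment".

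The arm used in the safety tables is fixed by protocol 6.8.2: "Patients will be included in the analyses according to the treatment they received".

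Protocol 6.4.1 describes how patients leave study treatment. Re-induction after a marrow with residual blasts is permitted, not required. For failures: "Patients who are not in CR at the end of re-induction will be taken off study". For transplant: "Patients who could benefit from and are eligible to undergo stem cell transplantation will go off the study at any time when transplant is feasible".

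On later treatment, SAP 7.4.2 says: "Post treatment medications are those with start date after the last dose of study drug". Protocol 6.8.6 planned to code and summarize post-treatment anti-AML therapy. SAP 7.4.2 and section 8 reduce this to a listing (Listing 16.2.12).

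**The concern.** Safety and tolerability with induction is one of the two primary objectives (protocol 5.1), and the by-arm TEAE tables in SAP 7.7.1 are its main evidence. A patient who stops study treatment and starts another intensive regimen within 30 days has two possible causes for any new severe event. The plan counts that event as treatment-emergent in the arm the patient was treated in and does not use the start date of the new regimen. With about 25 patients per arm, a few extra severe or fatal events can change how a descriptive table reads. No planned table shows by arm how many patients started other therapy inside the window, so a reader could not judge the overlap.

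**Working it through.** **Inputs from the documents**
- Window end = day of last study dose + 30 (protocol 6.8.10, SAP 7.7.1).
- Last planned induction dose: Day 7 (protocol 6.5.4).
- Marrow on Days 14-21. Without count recovery, remission is evaluated at about Day 35 after one course or about Day 49 after re-induction (protocol 6.4.1).
- 25 patients per arm; CR rates 0.55 (control) and 0.80 (dose arm) (protocol 6.8.1).

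**Assumptions**
- Other therapy starts the day after the marrow or evaluation.
- 7+3 re-induction starts on Days 15-22.

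**The plan's own figure.** The plan gives no figure for the safety window. Its one design figure is 71.8% power. Exact enumeration of two Binomial(25) outcomes with a one-sided Fisher test at 0.15 gives 71.7%, so it reproduces. It is not in dispute here.

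**Overlap** = window end − start of other therapy + 1, counting both days.

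1. *One induction, no re-induction, other therapy straight after the marrow.* Window end: 7 + 30 = Day 37. Start Day 22: 37 − 22 + 1 = 16 days. Start Day 15: 37 − 15 + 1 = 23 days. As shares: 16/37 = 43% and 23/37 = 62%.
2. *One induction, other therapy after the Day 35 evaluation.* Start Day 36: 37 − 36 + 1 = 2 days.
3. *7+3 re-induction, other therapy after the Day 49 evaluation (start Day 50).* Re-induction from Day 15: last dose Day 21, window end Day 51, overlap 51 − 50 + 1 = 2 days. From Day 22: last dose Day 28, window end Day 58, overlap 58 − 50 + 1 = 9 days.
4. *Range for case 3.* With 5+2 instead, window ends are Days 49 and 56, giving 0 and 7 days. Letting either regimen start anywhere on Days 14-28 gives 0-15 days.

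**Direction.** Let s be the share of non-CR patients who start salvage inside the window, and t the share of CR patients who start transplant conditioning inside it. The documents give neither. Expected patients affected per 25:

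- control: 25 × (0.45s + 0.55t)
- dose arm: 25 × (0.20s + 0.80t)
- difference: 25 × (0.25s − 0.25t) = 6.25 × (s − t)

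| s | t | control | dose arm |
|---|---|---|---|
| 0.25 | 0 | 2.8 | 1.3 |
| 0.50 | 0 | 5.6 | 2.5 |
| 0.25 | 0.25 | 6.25 | 6.25 |
| 0.10 | 0.25 | 4.6 | 5.5 |

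At the design rates, the sign of the difference depends only on whether s or t is larger.

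**The case against.** **The plan already separates some of this.** Each AE is asked whether underlying disease or other drugs could explain it (protocol 6.6.3.2.6). Table 14.3.1.5 summarizes those events, Tables 14.3.1.2 to 14.3.1.4 give events related to each study drug, and Table 14.3.1.12 splits TEAEs by relationship. The AE and medication listings carry start dates. This stands in part, because a determined reader could rebuild the split from listings. But the attribution is investigator judgment in an open-label trial, and it pools disease with other drugs. The main Grade 3 or higher, serious and fatal tables still contain the events.

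**Later therapy may already be tabulated.** Read literally, SAP 7.4.2 also makes any drug started after the first dose concomitant, so salvage could appear in the AML concomitant-medication table. That table would not show whether it began before or after a given AE.

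**Leaving the study may end AE collection.** The documents do not say. Collection is tied to the last study treatment, not to study status. If sites did stop early, time at risk would differ with outcome, which is a further reason to show it.

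**A fixed window has merit.** Cutting follow-up at new therapy shortens it selectively in failing patients and drops delayed study-drug toxicity. This stands, so the all-events tables should remain.

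**Stronger readings that a reader might infer.**
- *Control is made to look more toxic and CX-01 toxicity is masked.* At the design rates non-CR patients number 25 × 0.45 = 11.25 in control and 25 × 0.20 = 5 in a dose arm. These counts include CRi patients, early deaths and missing responses, so they are not counts of salvage starters. The synopsis also places transplant after documented CR, so conditioning may load the arm with more remissions.
- *Events are charged to the randomized arm.* Safety tables follow treatment received.
- *Overlap of 43-62% is typical.* It needs a patient to skip re-induction and start other therapy at once, a route no section describes.

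**Conclusion.** The gap is real and limited. Neither document stops or splits TEAE counting at non-protocol anti-AML therapy, and the design lets such therapy begin inside the 30 days. For patients who follow the planned evaluations the overlap is short: about 2 days after Day 35 and roughly 2-9 days after Day 49. Those evaluation days are approximate, so the overlap could also be nil. It is large (16-23 of 37 days) only for other therapy started directly after the Day 14-21 marrow.

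The conclusion assumes that AE collection continues to 30 days after a patient leaves study treatment. The number affected and the direction between arms cannot be derived from the documents, so no bias for or against CX-01 can be claimed. This concerns the clarity of a descriptive safety analysis in an exploratory phase II trial, though one that serves a primary objective.

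**What to change.** Keep the planned all-events TEAE tables. In SAP 7.7.1:

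- Add a derived flag for AEs with onset on or after the first recorded non-protocol anti-AML therapy, including transplant conditioning where its date is recorded.
- In the overall, Grade 3 or higher, serious and fatal TEAE tables, show events before and after that date in separate rows, by arm as treated.
- Report, by arm as treated, the number of patients starting such therapy inside the window and the days at risk before it.

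Medication use is recorded until the Safety Follow-Up Visit (protocol 6.4.5), and Listing 16.2.12 already carries start date and indication, so the flag needs no new medication data. No section names a conditioning date, so that part depends on what was captured.

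The cost is a little more programming. Delayed study-drug toxicity with onset after new therapy will sit in the later row, which is why the all-events tables stay. Treatment rules, AE collection, the primary endpoint, sample size and power do not change.

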6.8.10.2 Clinical Laboratory Assessments

Clinical laboratory assessment will be summarized using frequency tables, shift tables, and descriptive statistics. Frequency tables and shift tables will be presented by NCI-CTCAE grade. Laboratory variables with no NCI-CTCAE group will be presented in shift tables with respect to normal range. All laboratory variables will be presented in tables of descriptive statistics (mean, SD, etc.) and in graphs.

6.8.10.3 Vital Signs and ECOG Performance Status

Vital signs variables and ECOG performance status will be summarized using descriptive statistics.

6.8.10.4 Electrocardiogram

Electrocardiogram will be summarized using descriptive statistics.

6.8.11 Pharmacokinetic Analysis

The PK parameters will be summarized by descriptive statistics. A list of PK parameters and definitions will be specified in the SAP.

7. RISKS AND BENEFITS

The potential risks associated with participation in this study are minimal based on available safety data. Such risks are limited to unforeseen adverse interactions between idarubicin + cytarabine and CX-01. Heparins, as a class are associated with abnormal LFTs, which are generally reversible and of little clinical importance.

Study participants may benefit from participating in the trial if, by mobilizing AML stem cells from the protective environment of the bone marrow or through other mechanisms, the addition of CX-01 at either of two dose levels results in an enhanced cytotoxic effect of idarubicin + cytarabine, although such benefit is not guaranteed.

For further details concerning warnings, precautions, and contradictions, refer to the appropriate section of the IB (63).

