4.3 Summary of Studies with CX-01

4.3.1 Preclinical Data

In rats the no-observed-adverse-effect-level (NOAEL) was 48 mg/kg/day, and in dogs it was 160 mg/kg/day. The only observed adverse effect in either species was the expected

occurrence of hemorrhage at high doses of drug, when coagulation parameters were prolonged. No adverse effect on cardiac conduction has been observed in porcine studies of myocardial infarction. There were no adverse effects of CX-01 administration on the cardiovascular profile in dogs or on the respiratory parameters in albino rats.

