PGX-ODSH-2006	II	Exacerbation of COPD	N=156, equally randomized to receive standard treatment of COPD with or without CX-01	CX-01 given as a 8 mg/kg bolus followed by CX-01, 0.375 mg/kg/h for 96 hours	
Primary Composite of failure to discharge from hospital in a timely manner + relapse within 21 days of hospital discharge
 
Secondary FEV₁, FEV₁/FVC, Borg CR10Scale, 6-minute Walk Test, BODE index and hs-CRP
	
There was no evidence of effect or efficacy of CX-01 compared to placebo for the primary endpoint for Intent-to-Treat (ITT) or Per Protocol (PP) Populations. No statistical significant effects were shown for the secondary endpoints.
 
CX-01 was well tolerated. A few instances of minor/moderate bleeding and only one case of major bleeding. Some predictable changes were noted for AST and ALT with CX-01 treatment. No other clinical and laboratory parameters showed

Study Number	Phase	Indication	Number of Patients	Study Drug and Dose	Study Endpoints	Study Results
						significant changes from baseline. Eight deaths were reported (placebo=5 and CX-01=3). Those three were not related to CX-01 occurred post treatment.
PGX-ODSH-2009-PLE	II	Protein losing enteropathy (PLE) secondary to Fontan procedure	N=5, Pediatric and young adult population	CX-01, 96 hour IV infusion at 0.125 mg/kg/h or CX-01, 96 hour IV infusion at 0.250 mg/kg/h	Safety, reduction of symptoms of PLE, reduction of alpha-1 antitrypsin levels	Though all patients had some subjective clinical improvement, CX-01 did not show clear effects on efficacy biomarkers. Due to extremely low patient enrollment and a lack of efficacy, the study was terminated early. 22 AEs and two unrelated SAEs were reported. All AEs were considered mild or moderate in intensity.

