- CX-01 will be temporarily discontinued in patients who develop aPTT above 45 seconds during continuous infusion of CX-01 and at least 8 hours after the bolus dose of CX-01, until the aPTT is <35 seconds. CX-01 will then be resumed at a 50% dose reduction. If the aPTT rises above 45 seconds at the reduced dose, CX-01 will be permanently discontinued. If aPTT at the 50% reduced dose is <35 seconds, 4 hours or more after dose reduction, the dose can be escalated by 25%. If the aPTT after dose escalation again rises above 45 seconds at the reduced dose, the CX-01 will be temporarily discontinued until the aPTT is <35 seconds, and then resumed at the previous 50% dose reduction.
- Abnormal liver function:
 - If Grade 1 increases in AST, ALT, or bilirubin occur (e.g., increase in AST or ALT from ULN to 3.0 x ULN; increase in total bilirubin from ULN to 1.5 x ULN), the frequency of liver function testing will be increased, if the Investigator judges that the laboratory abnormalities are potentially related to study treatment. No reduction of dose is required
 - If Grade 2 increases in AST, ALT, or bilirubin occur (e.g., increase in AST or ALT to >3.0 to 5 x ULN; increase in total bilirubin from >1.5 to 3 x ULN), the frequency of liver function testing will be increased to \geq once a week, if the Investigator judges that the laboratory abnormalities are potentially related to study treatment. No reduction of dose is required
 - If Grade 3 increases in AST, ALT, or bilirubin occur (e.g., increase in AST or ALT to >5.0 to 20 x ULN; increase in total bilirubin from >3.0 to 10 x ULN) and if the Investigator judges that the laboratory abnormalities are potentially related to study treatment, study drug must be stopped. Frequent laboratory evaluations (more than once weekly) will be

conducted until liver function tests return to Grade 1 or baseline value. Study treatment will be resumed after liver function tests return to Grade 1 or baseline value provided administration of chemotherapy is in progress. If resumption of study treatment is considered for subjects who have experienced Grade 3 increases in AST, ALT, or bilirubin liver function will be monitored at least daily during CX-01 infusion

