- If Grade 4 increases in AST, ALT, or bilirubin occur (e.g., increase in AST or ALT to >20 x ULN; increase in total bilirubin to >10 x ULN) and if the Investigator judges that the laboratory abnormalities are potentially related to study treatment, the patient must discontinue study treatment immediately and will not be re-challenged. The patient will be followed until resolution of abnormal liver function tests.
- Renal function:

If the calculated creatinine clearance drops below 30 mL/min/1.73m² prior to or during dosing with CX-01, the dose of CX-01 will be held until the creatinine clearance rises above 30 mL/min/1.73m².
- For any other Grade 3 or 4 toxicities that appear to be related to CX-01 during either the induction or consolidation cycles, CX-01 will be interrupted until the AE resolves to Grade 1 or less, and then resumed at 0.125 mg/kg/hour provided administration of chemotherapy is in progress. If CX-01 is interrupted for greater than 72 hours, the patient will be discontinued from treatment. If the AE recurs at a level of Grade 3 or higher, the CX-01 will be discontinued.

This study will utilize the National Cancer Institute-Common Terminology Criteria for Adverse Events (NCI-CTCAE) Version 4.03 for AE and SAE reporting. A copy of the CTCAE Version 4.03 can be downloaded: (<http://safetyprofiler.ctep.nci.nih.gov/CTC/CTC.aspx>).

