6.4.5.1 Permitted Concomitant Medications

Refer to Section 6.4.1.1 for transfusion parameters. Treatment for disease-related symptoms and drug-related toxicities are expected as standard of care and should be recorded in the patient's medical record and eCRF.

The use of myelopoietic growth factors (G-CSF and GM-CSF) is allowed, consistent with the Investigator's clinical judgment and institutional guidelines.

6.4.5.2 *Prohibited Concomitant Medications*

Patients are not permitted to take those medications specified in the exclusion criteria (Section 6.3.2).

The following medications are prohibited:

- Any anticoagulation therapy (with the exception of heparin flushes). CX-01 IV bolus doses may cause a slight transient increase of aPTT (to approximately 60 seconds) for less than 1 hour, while the continuous IV infusion at the doses to be used in this study, based upon previous studies, will raise the aPTT to the ULN or to a level (approximately 35 to 45 seconds) that is not of clinical significance. CX-01 may, however, potentiate the anticoagulation effect of UFH, LMWH or anticoagulants if administered concomitantly. Therefore, concomitant administration of CX-01 with other anticoagulants will not be permitted in patients participating in this study other than as heparin flushed to maintain IV line patency.
- Any investigational therapeutic agents.

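### CX-01's fixed 0.125 mg/kg/hour restart gives Group 2 no dose reduction, a Grade 3-4 bleed judged unrelated has no mandatory hold, and Section 7 states the risks too absolutely

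*Protocol*

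**What the plan says.** **Risk statement.** Protocol Section 7 calls the risks minimal and states: "Such risks are limited to unforeseen adverse interactions between idarubicin + cytarabine and CX-01". It adds reversible liver-test changes as a heparin class effect and refers to the Investigator's Brochure. It does not mention bleeding.

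**Bleeding data elsewhere.** Section 4.3.1 gives one adverse effect in animals, the expected "occurrence of hemorrhage at high doses of drug, when coagulation parameters were prolonged". Table 4-1 reports for the COPD study "A few instances of minor/moderate bleeding and only one case of major bleeding", on the regimen "CX-01 given as a 8 mg/kg bolus followed by CX-01, 0.375 mg/kg/h for 96 hours". The table does not say in which arm the bleeds occurred.

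**Expected aPTT.** Section 6.4.5.2 says the infusion "will raise the aPTT to the ULN or to a level (approximately 35 to 45 seconds) that is not of clinical significance".

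**Dose rules (6.4.4.2).** An aPTT above 45 seconds, at least 8 hours after the bolus, stops the infusion; once aPTT is below 35 seconds, "CX-01 will then be resumed at a 50% dose reduction". Liver tests and creatinine clearance have their own rules. Everything else falls under a residual rule that begins "For any other Grade 3 or 4 toxicities that appear to be related to CX-01". Under it CX-01 is interrupted until Grade 1 or less "and then resumed at 0.125 mg/kg/hour provided administration of chemotherapy is in progress". An interruption over 72 hours ends treatment, and a recurrence at Grade 3 or higher ends CX-01. No rule is specific to bleeding.

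**The concern.** CX-01 is a heparin derivative infused for 5 to 7 days in patients whose platelets are falling from AML and chemotherapy. Safety and tolerability is a primary objective. Three features of the text sit badly with that.

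- The residual rule names one restart rate for two arms with different assigned rates. The reduction after a related Grade 3-4 toxicity therefore depends on the arm, and in Group 2 it is nil.
- The aPTT trigger starts where the expected range ends. A serious bleed at an expected aPTT reaches only the residual rule, so one patient-level relatedness judgment decides whether the infusion must stop. That judgment is uncertain in a thrombocytopenic patient.
- Section 7 presents as unforeseen a class of risk that the dose rules, the anticoagulant ban and the safety analysis all anticipate.

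**Working it through.** **Inputs.** Assigned rates are 0.125 (Group 2) and 0.25 mg/kg/hour (Group 3), with a 4 mg/kg bolus and 7 days (168 hours) of induction infusion (Protocol 6.4.1). Interrupted time is not made up (6.4.1.5).

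**The plan's own figures.** 0.125 × 24 = 3 mg/kg/day and 0.25 × 24 = 6 mg/kg/day, as in SAP 7.5. Full induction dose: Group 2, 4 + 0.125 × 168 = 25 mg/kg; Group 3, 4 + 0.25 × 168 = 46 mg/kg.

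**Restart rate as a fraction of the assigned rate.**
- Residual rule: Group 2, 0.125/0.125 = 100%; Group 3, 0.125/0.25 = 50%.
- aPTT rule: 50% in both (0.0625 and 0.125).
- Group 2 patient already at 0.0625 under the aPTT rule who then meets the residual rule: 0.125/0.0625 = 2, a doubling if read literally.

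**Dose delivered.** For a hold of H hours starting at hour h, remaining time R = max(0, 168 − h − H), and dose = 4 + assigned rate × h + restart rate × R. The documents give no typical hold length, so H is varied up to the 72-hour limit. The three values in each cell are for h = 24, 72 and 120 (end of Days 1, 3 and 5), in mg/kg.

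| Hold | Group 2, current (of 25) | Group 2, restart at 0.0625 | Given up in Group 2 | Group 3, current (of 46) |
|---|---|---|---|---|
| 24 h | 22, 22, 22 (88%) | 14.5, 17.5, 20.5 (58%, 70%, 82%) | 7.5, 4.5, 1.5 | 25, 31, 37 (54%, 67%, 80%) |
| 48 h | 19, 19, 19 (76%) | 13, 16, 19 (52%, 64%, 76%) | 6, 3, 0 | 22, 28, 34 (48%, 61%, 74%) |
| 72 h | 16, 16, 19 (64%, 64%, 76%) | 11.5, 14.5, 19 (46%, 58%, 76%) | 4.5, 1.5, 0 | 19, 25, 34 (41%, 54%, 74%) |

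Example, Group 2, h = 24, H = 24, so R = 120: current 4 + 3 + 0.125 × 120 = 22; at half rate 4 + 3 + 0.0625 × 120 = 14.5.

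**Which rule reaches a bleed?**
- aPTT above 45 seconds: the aPTT rule, whatever the attribution.
- aPTT 45 seconds or less, Grade 3-4, appears related: the residual rule.
- aPTT 45 seconds or less, Grade 3-4, judged unrelated: no mandatory hold. Section 6.3.3 permits stopping but does not require it.

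**How close are the bleeding data to this trial?** COPD against Group 3 induction: bolus 8/4 = 2 times; rate 0.375/0.25 = 1.5 times; total 8 + 0.375 × 96 = 44 against 46 mg/kg, but over 96 rather than 168 hours. If the major bleed was among the 78 patients on CX-01, which is an assumption, the rate is 1/78 = 1.3% (exact 95% CI 0.03% to 6.9%).

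**The case against.** **Section 7 speaks about this study's doses.** The animal bleeding was at high doses. The COPD regimen had twice Group 3's bolus and 1.5 times its rate, and the arm is not stated. Section 4.2 puts the start of an anticoagulant effect at about twice the plasma concentrations reached before, so the similar cumulative dose is a weak link. The closest evidence is favorable: the AML pilot used Group 3's regimen with the same chemotherapy in 12 patients, and the protocol reports good tolerability, no associated serious events and mean aPTT largely in the mid-30s (Table 4-1, 6.4.4.1). The three serious events listed for the 35 pancreatic-cancer patients on CX-01 include no bleed. This stands. A reader might infer that the protocol's data show excess bleeding at study doses, or that patients were not told; the documents support neither. The Brochure is not available and the consent pages were removed. However, 12 patients leave wide uncertainty: with no related serious bleed in 12, the one-sided 95% upper limit is 1 − 0.05^(1/12) = 22%.

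**Bleeding is managed elsewhere.** There are entry exclusions, an anticoagulant ban, frequent PT/aPTT checks, platelet transfusion, a monitoring committee and focused bleeding summaries. Section 6.6.3.2.1 says adverse events will be treated appropriately, including by changes in study drug. The relatedness question asks only for a reasonable possibility (6.6.3.2.6), which a serious bleed on a heparin derivative could readily meet. This too stands: the missing hold is a narrow gap, not a demonstrated error. A reader might also infer that blaming thrombocytopenia releases a bleed from the hold. It does not, because causality from CX-01 and explanation by disease or other drugs are separate questions.

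**The restart may be a deliberate floor.** A rate of 0.125 is the lowest infusion rate given before (4.3.2). But the aPTT rule already takes Group 2 to 0.0625, so the protocol does not treat 0.125 as a floor.

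**Conclusion.** The point holds, with most weight on the restart rule. After a related Grade 3-4 toxicity the rate falls 50% in Group 3 and 0% in Group 2, and can rise for a Group 2 patient already reduced for aPTT. The restart remains subject to resolution, chemotherapy in progress, the 72-hour limit and the recurrence stop. The 88% delivered in Group 2 applies to a 24-hour hold only; it is 76% at 48 hours and 64% to 76% at 72 hours.

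The bleed gap is real but narrow: Grade 3-4, aPTT of 45 seconds or less, judged unrelated, and an investigator who continues. The documents give no frequency for it. Section 7's wording is too absolute and needs correcting, but the protocol recognizes the anticoagulant effect elsewhere.

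One clerical mismatch lies alongside: the pancreatic-study infusion is 5 days in 6.4.4.1 and 48 hours in Table 4-1.

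**What to change.** 1. **6.4.4.2, restart.** Resume at 50% of the assigned rate (0.125 mg/kg/hour in Group 3, 0.0625 in Group 2) and never above the rate in use before the hold. Keep the existing resolution, chemotherapy, 72-hour and recurrence conditions.
2. **6.4.4.2, bleeding (a cheap improvement).** Hold CX-01 for any Grade 3 or higher bleed or any CNS bleed, whatever the attribution or aPTT.
3. **Section 7.** Name bleeding and anticoagulant effect as a foreseeable risk, citing the COPD bleeding with its higher bolus and rate, and the pilot's tolerability.
4. **6.4.4.1.** Make the pancreatic infusion length agree with Table 4-1.

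**Cost.** A protocol amendment, with no new assessments and no change to sample size. The lower restart costs an affected Group 2 patient a further 1.5 to 7.5 mg/kg (6% to 30% of 25) with a 24-hour hold, and less with longer holds. For the bleed hold, assume that 2% to 10% of CX-01 patients (1 to 5 of 50) trigger it. Mean induction exposure per arm then falls by between 0.02 × 18% = 0.4% (Group 2, hour 120, 24-hour hold, half-rate restart) and 0.10 × 78% = 7.8% (Group 3, hour 24, no restart: 10 of 46 mg/kg delivered). Some of these patients would be held under the present rule anyway. A bleed hold over 72 hours would bring in the existing discontinuation rule. SAP Section 5 excludes patients who breach dose-modification rules from the per-protocol set, so the new rules change who qualifies and that definition should refer to them.
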